13.1 Appendix: Schedule of Events

Table 13-1 Schedule of Events

Procedure	Screening Period	Treatment Period 1						Treatment Period 2: Dose Tapering Period	Follow-Up
		Visit 1	Visit 2	Telephone Contact	Visit 3	Telephone Contact	Visit 4		
Visit	Visit 1	Visit 2	Telephone Contact	Visit 3	Telephone Contact	Visit 4	Visit 5	Visit 6 / Early Termination Visit	Visit 7
Study Days	-28 to -6	1	2 to 6 ^a	7	12 or 13 or 14 ^a	21	28	42	56
Visit Window				± 2 days		± 2 days	± 2 days	± 5 days	± 5 days
Informed consent	X								
Medical history	X								
Inclusion/exclusion criteria	X								
Video EEG ^b	X						X		
BASED Score	X						X		
Demographics	X								
12-lead electrocardiogram	X			X			X	X	
Urine drug screen ^c	X								
Physical and neurological examination ^d	X	X	X ^e	X		X	X	X	X
Vital sign measurements ^f	X	X		X		X	X	X	X
Clinical laboratory tests ^g	X			X			X	X	
Investigational product administration ^h		X	X	X	X	X	X		

Procedure	Screening Period	Treatment Period 1						Treatment Period 2: Dose Tapering Period	Follow-Up
		Visit 1	Visit 2	Telephone Contact	Visit 3	Telephone Contact	Visit 4		
Visit	Visit 1	Visit 2	Telephone Contact	Visit 3	Telephone Contact	Visit 4	Visit 5	Visit 6 / Early Termination Visit	Visit 7
Study Days	-28 to -6	1	2 to 6 ^a	7	12 or 13 or 14 ^a	21	28	42	56
Visit Window				± 2 days		± 2 days	± 2 days	± 5 days	± 5 days
Dispensing of investigational product		X		X		X	X		
Investigational product accountability assessment				X		X	X	X	X
Adverse event monitoring		X	X	X	X	X	X	X	X
Review of prior and concomitant medications ^j	X	X	X	X		X	X	X	X
Clinical Global Impression of Change ^m		X		X		X	X	X	
Seizure diary ^j	X	X	X	X	X	X	X	X	
Pharmacokinetic blood sampling ^k		X				X			
Pharmacokinetic urine sampling ^l		X				X			

Abbreviations: EEG, electroencephalogram

- The investigator or his/her delegate will follow-up by telephone or email on Day 2 to Day 6 to ensure that the seizure diary is being completed, to review seizure counts, and to conduct daily assessments. The investigator will also contact the parent/caregiver by telephone on Day 12, or Day 13 or Day 14 to review seizure counts and to assess the patient's status.
- An overnight video-EEG will be completed within the Screening Period (Days -28 to -6), and repeated at Day 28 (Visit 5 [± 2 days]), [REDACTED]
[REDACTED]
- Urine drug screen assessment to test for the presence of cannabinoids will be performed locally.
- A complete physical examination will include assessment of skin, head, ears, eyes, nose, throat, neck, thyroid, lungs, heart, cardiovascular,

abdomen, lymph nodes, and musculoskeletal system/extremities. Where possible, a neurological examination will include mental status evaluation, examination of cranial nerves, motor examination (muscle tone, strength, and reflexes), cerebellar examination (coordination and gait), and sensory examination. Physical and neurological examination will also be conducted on Day 2 prior to discharge.

- e. After physical and neurological examination is conducted on Day 2, physical and neurological examination is not scheduled to be conducted again until Day 7 (Visit 3 [\pm 2 days]).
- f. Vital signs measurements will include blood pressures, temperature (measured rectally), pulse rate, and respiratory rate. Height, weight, and body mass index (BMI) will be measured at each clinic visit. Vital sign measurements will also be conducted on Day 2, prior to discharge.
- g. Includes urinalysis. Hematology, coagulation and serum chemistry assessments will be performed by the sponsor's central laboratory; urinalysis assessment will be performed locally.
- h. Investigational product will be administered orally twice daily, in the morning and 12 hours after the morning dose at a dose of 6 mg/kg after at least a 2-hour fast during the first 7 days of Treatment Period 1. Starting from the PM dose on the day of Visit 3, the dose will be escalated and patients will receive the investigational product at a dose of 9 mg/kg orally twice daily. Starting on Day 15, the dose will be escalated again and patients will receive the investigational product at a dose of 15 mg/kg orally twice daily until the end of Treatment Period 1. The first 2 doses of the investigational product (6 mg/kg orally) will be administered during Visit 2 and the remaining doses will be administered at home. Patients will receive investigational product up to Day 28 (Treatment Period 1). Following Treatment Period 1, Treatment Period 2 (Dose Tapering Period) will begin on Day 29 and the dose will be reduced by half for all patients. On Day 35, the dose will be reduced by half again, and on Day 42, the investigational product will be stopped.
- i. Prior medications will be recorded during the Screening Period. All medications taken by patients after Screening Period until the completion of the final Follow-Up visit will be documented as concomitant medications.
- j. Seizure diary will be distributed on the Screening Period visit (Visit 1). The investigator will ensure that the seizure diary is being completed. The investigator will also review seizure counts to make sure seizures are not increasing. The seizure diaries will indicate whether spasms are still present. [REDACTED]
- k. Details regarding PK blood sampling are provided in [Table 13-2](#).
- l. Urine sampling for PK assessment will be collected by using a plastic urine collection bag following the morning dosing of investigational product on Day 1 and Day 21 (Visit 4 [\pm 2 days]).
- m. The Clinical Global Impression of Change is completed by both the Investigator and the Caregiver. CGI-C on Day 1 is performed prior to dosing.

13.2 Appendix: Pharmacokinetic Sampling

Table 13–2 Steady State Pharmacokinetic Sampling Time Points

Study Period		Blood Sampling Time Points ^a
Visit	Study Days	
2 ^b	1	
 • 0.5-1.5 hours post-AM dose • 4-6 hours post-AM dose • 8 hours post-AM dose time point and pre-PM dose
4 ^b	21	
 • 0.5-1.5 hours post-AM dose • 4-6 hours post-AM dose • 8 hours post-AM dose time point and pre-PM dose

a. The PK blood sampling scheme may be modified on a case-by-case basis so as not to exceed a total blood draw limit of 8 mL/kg over 56 days, to a maximum blood draw of 50 mL. Note that the total blood drawn accounts for both blood draws for PK assessment as well as other assessments (i.e., clinical laboratory assessments).

b. The AM dose should be administered at the clinical site prior to the PK blood sampling on Visit 2 & 4.

13.3 Appendix: List of Excluded Medications

- alfentanil
- alprazolam
- amlodipine
- aprepitant
- aripiprazole
- astemizole
- atorvastatin
- avanafil
- boceprevir
- budesonide
- buspirone
- carbamazepine
- cafergot
- cerivastatin
- chlorpheniramine
- cilostazol
- cisapride
- clarithromycin
- codeine-N-demethylation
- colchicine
- conivaptan
- cyclosporine
- dapsone

- darifenacin
- darunavir
- dasatinib
- dexamethasone
- dextromethorphan
- diazepam
- diltiazem
- docetaxel
- domperidone
- dronedarone
- ebastine
- eletriptan
- eliglustat
- eplerenone
- erythromycin
- estradiol
- everolimus
- felodipine
- fentanyl
- finasteride
- gleevec
- haloperidol
- hydrocortisone
- ibrutinib
- indinavir

- irinotecan
- lercanidipine
- levo- α -acetylmethadol
- lidocaine
- lomitapide
- lovastatin
- lurasidone
- maraviroc
- methadone
- midazolam
- naloxegol
- nateglinide
- nelfinavir
- nevirapine
- nifedipine
- nisoldipine
- nitrendipine
- ondansetron
- pimozide
- prednisolone
- prednisone
- progesterone
- propranolol
- quetiapine
- quinidine

- quinine
- rilpivirine
- risperidone
- ritonavir
- rivaroxaban
- romidepsin
- salmeterol
- saquinavir
- sildenafil
- simvastatin
- sirolimus
- sorafenib
- sunitinib
- tacrolimus
- tadalafil
- tamoxifen
- taxol
- telaprevir
- telithromycin
- terfenadine
- testosterone
- ticagrelor
- tipranavir
- tolvaptan
- torisel

- trazodone
- triazolam
- vardenafil
- vemurafenib
- verapamil
- vincristine
- zaleplon
- ziprasidone
- zolpidem

13.4.1 Regulatory History and Overview

This revision is effective on 15 September 2020, and will be submitted to all applicable Institutional Review Boards (IRBs), Independent Ethics Committees (IECs), or Research Ethics Boards (REBs), and Regulatory Authorities.

Table 13-3: Summary of Protocol CL-0101-WS01 Revision History

Version and Date	Reason for Revision
Revision 1.0 March 1, 2019	Initial protocol to support Phase 2 study entitled: A Phase 2 Study to Assess the Safety, Tolerability, Exploratory Efficacy, and Pharmacokinetics of Orally Administered JBPOS0101 for Refractory Infantile Spasms Patients (Protocol Number CL-0101-WS01).
Revision 1.1 May 15, 2019	[REDACTED]
Revision 1.2 September 19, 2019	[REDACTED]
Revision 1.3 April 9, 2020	[REDACTED]
Revision 2.0 September 15, 2020	[REDACTED]

13.4.2 Summary of Changes

The following changes have been made to the protocol entitled *A Phase 2 Study to Assess the Safety, Tolerability, Exploratory Efficacy, and Pharmacokinetics of Orally Administered JBPOS0101 for Refractory Infantile Spasms Patients* (Protocol Number CL-0101-WS01), Revision 1.3, dated 9 April 2020:

Protocol Section	Description of Change
General	
Version and date updated throughout the document from Version 1.3, 9 April 2020 to Version 2.0, 15 September 2020
Protocol Synopsis	[REDACTED]
List of Abbreviations	
[REDACTED]
3.1 Study Design	[REDACTED]
4.1.1 Inclusion Criteria	[REDACTED]
4.1.2 Exclusion Criteria	[REDACTED]

Protocol Section	Description of Change
5.3.1 Investigational Product Packaging and Storage	[REDACTED]
6.2.1 Pharmacokinetic Blood and Urine Samples	[REDACTED]
6.4 Safety Monitoring Committee	[REDACTED]
7.4 Sample Size Calculations	[REDACTED]
7.5 Analysis Sets	[REDACTED]
13.1 Appendix: Schedule of Events	[REDACTED]

## LIST OF ABBREVIATIONS

Abbreviation	Definition
AE	adverse event
AEDs	anti-epileptic drugs
ATC	anatomical therapeutic chemical
AUC	area under the plasma concentration-time curve
BASED	burden of amplitudes and epileptiform discharges
BID	twice daily
BLQ	Below limit of quantification
BMI	body mass index
CI	confidence interval
CGI-C	clinical global impression of change
C max	maximum plasma concentration
C min	minimum plasma concentration
CSR	clinical study report
CV	coefficient of variation
DMP	data management plan
EAS	efficacy analysis set
ECG	electrocardiogram
eCRF	electronic case report form
EEG	electroencephalogram
FDA	Food and Drug Administration
GCP	Good Clinical Practices
GM	geometric mean
HR	heart rate
ICF	informed consent form
ICH	International Council for Harmonization
IS	infantile spasms
LFT	liver function tests
mEAS	Modified efficacy analysis set
MedDRA	Medical Dictionary for Regulatory Activities
NONMEM	Non-linear Mixed Effects Modeling
OTC	over-the-counter
PK	pharmacokinetic(s)
PT	preferred term
Q1	quartile 1

Abbreviation	Definition
Q3	quartile 3
QTcF	QT interval from Fridericia's formula
SAE	serious adverse event
SAP	statistical Analysis Plan
SD	standard deviation
SOC	system organ class
SQRT	square root
TEAE	treatment-emergent adverse event

## **1 INTRODUCTION**

This statistical analysis plan (SAP) is consistent with the statistical methods section of the final study protocol (Version 2.0, dated 15 September 2020) and includes additional detail of safety, tolerability, exploratory efficacy and pharmacokinetic (PK) summaries to be included in the clinical study report (CSR).

## 2 STUDY OBJECTIVES AND ENDPOINTS

## 2.1 Primary Objectives

- To evaluate the safety and tolerability of the investigational product in patients with refractory Infantile Spasms (IS).

## 2.2 Secondary Objective

- To characterize the PK of the investigational product in patients with refractory IS.

## 2.3 Exploratory Objective

- To evaluate the efficacy of the investigational product in treating patients with refractory IS.

## 2.4 Study Endpoints

### 2.4.1 Primary Safety Endpoints

- Incidence of Treatment emergent Adverse Events (TEAEs)
- Vital signs
- Electrocardiograms (ECGs)
- Physical and Neurological examinations
- Clinical laboratory assessments

## 2.4.2 PK Endpoints

- Primary PK endpoints include plasma PK parameters: area under the concentration-time curve (AUC), minimum plasma concentration ( $C_{\min}$ ) and maximum plasma concentration ( $C_{\max}$ )
- Relationship between plasma investigational product levels and response

### 2.4.3 Exploratory Efficacy Endpoints

A horizontal bar chart with 10 categories on the y-axis and sample counts on the x-axis. Category 0 has 1000 samples. Category 1 has 999 samples. Category 2 has 998 samples. Category 3 has 1 sample. Category 4 has 1000 samples. Category 5 has 999 samples. Category 6 has 1000 samples. Category 7 has 999 samples. Category 8 has 1000 samples. Category 9 has 999 samples. Category 10 has 1 sample.

Category	Sample Count
0	1000
1	999
2	998
3	1
4	1000
5	999
6	1000
7	999
8	1000
9	999
10	1

### **3 STUDY DESIGN**

#### **3.1 General**

This is an open-label, multicenter study to evaluate the safety, tolerability, PK, and exploratory efficacy of the investigational product in children aged 6 months through 36 months with IS. Patients will receive the investigational product at a dose of 6 mg/kg orally twice daily (BID); once in the morning and 12 hours following the morning dose during the first 7 days of Treatment Period 1. Starting from the PM dose on the day of Visit 3, the dose will be escalated and patients will receive the investigational product at a dose of 9 mg/kg orally twice daily. Starting on Day 15, the dose will be escalated again and patients will receive the investigational product at a dose of 15 mg/kg orally twice daily until the end of Treatment Period 1. █

Table 3-1 Schedule of Event.

[figure not shown]
The overall study duration is expected to be up to 84 days ( $\pm$  5 days). As illustrated in [Figure 3-1](#), the study is planned to include 4 periods: Screening Period (up to 28 days), Treatment Period 1 (28 days), Treatment Period 2 (Dose Tapering Period [14 days]), and a Follow-Up Period (14 days). There will be a total of 7 study visits and 6 telephone/email contacts. Overall, the study includes 3 overnight stays: one for screening procedures, one for Day 1 (Visit 2) PK sampling and AE monitoring, and one for Day 28 (Visit 5 [ $\pm$  2 days]) video-EEG recordings.

During the Screening Period, Treatment Period 1, and Treatment Period 2, no changes to dosages of any drugs used for treating epileptic seizures are permitted (except for rescue medications used for acute treatment of breakthrough seizures which are not known to be CYP3A4 substrates and whose PK has not been shown to be impacted in the presence of a CYP3A4 inhibitor). Changes of dosages of drugs used for treating epileptic seizures are permitted 2 or more days after the investigational product has been discontinued.

The study design of the study is depicted in [Figure 3-1](#).

**Figure 3-1**

**Figure 3-1**

**Error! Reference source not found. Table 3-1 Schedule of Events**

Procedure	Screening Period	Treatment Period 1						Treatment Period 2: Dose Tapering Period	Follow-Up
		Visit 1	Visit 2	Telephone Contact	Visit 3	Telephone Contact	Visit 4		
Visit	Visit 1	Visit 2	Telephone Contact	Visit 3	Telephone Contact	Visit 4	Visit 5	Visit 6 / Early Termination Visit	Visit 7
Study Days	-28 to -6	1	2 to 6 a	7	12 or 13 or 14 a	21	28	42	56
Visit Window				± 2 days		± 2 days	± 2 days	± 5 days	± 5 days
Informed consent	X								
Medical history	X								
Inclusion/exclusion criteria	X								
Video EEG b	X						X		
BASED Score	X						X		
Demographics	X								
12-lead electrocardiogram	X			X			X	X	
Urine drug screen c	X								
Physical and neurological examination d	X	X	X e	X		X	X	X	X
Vital sign measurements f	X	X		X		X	X	X	X
Clinical laboratory tests g	X			X			X	X	
Investigational product administration h		X	X	X	X	X	X		

Procedure	Screening Period	Treatment Period 1						Treatment Period 2: Dose Tapering Period	Follow-Up
		Visit 1	Visit 2	Telephone Contact	Visit 3	Telephone Contact	Visit 4		
Visit									
Study Days	-28 to -6	1	2 to 6 a	7	12 or 13 or 14 a	21	28	42	56
Visit Window				± 2 days		± 2 days	± 2 days	± 5 days	± 5 days
Dispensing of investigational product		X		X		X	X		
Investigational product accountability assessment				X		X	X	X	X
Adverse event monitoring		X	X	X	X	X	X	X	X
Review of prior and concomitant medications j	X	X	X	X		X	X	X	X
Clinical Global Impression of Change m		X		X		X	X	X	
Seizure diary j	X	X	X	X	X	X	X	X	
Pharmacokinetic blood sampling k		X				X			
Pharmacokinetic urine sampling l		X				X			

Abbreviations: EEG, electroencephalogram

- The investigator or his/her delegate will follow-up by telephone or email on Day 2 to Day 6 to ensure that the seizure diary is being completed, to review seizure counts, and to conduct daily assessments. The investigator will also contact the parent/caregiver by telephone on Day 12, or Day 13 or Day 14 to review seizure counts and to assess the patient's status.
- An overnight video-EEG will be completed within the Screening Period (Days -21 to -6), and repeated at Day 28 (Visit 5 [± 2 days]).
- Urine drug screen assessment to test for the presence of cannabinoids will be performed locally.
- A complete physical examination will include assessment of skin, head, ears, eyes, nose, throat, neck, thyroid, lungs, heart, cardiovascular,

abdomen, lymph nodes, and musculoskeletal system/extremities. Where possible, a neurological examination will include mental status evaluation, examination of cranial nerves, motor examination (muscle tone, strength, and reflexes), cerebellar examination (coordination and gait), and sensory examination. Physical and neurological examination will also be conducted on Day 2 prior to discharge.

- e. After physical and neurological examination is conducted on Day 2, physical and neurological examination is not scheduled to be conducted again until Day 7 (Visit 3 [ $\pm$  2 days]).
- f. Vital signs measurements will include blood pressures, temperature (measured rectally), pulse rate, and respiratory rate. Height, weight, and body mass index (BMI) will be measured at each clinic visit. Vital sign measurements will also be conducted on Day 2, prior to discharge.
- g. Includes urinalysis. Hematology, coagulation and serum chemistry assessments will be performed by the sponsor's central laboratory; urinalysis assessment will be performed locally.
- h. Investigational product will be administered orally twice daily, in the morning and 12 hours after the morning dose at a dose of 6 mg/kg after at least a 2-hour fast during the first 7 days of Treatment Period 1. Starting from the PM dose on the day of Visit 3, the dose will be escalated and patients will receive the investigational product at a dose of 9 mg/kg orally twice daily. Starting on Day 15, the dose will be escalated again and patients will receive the investigational product at a dose of 15 mg/kg orally twice daily until the end of Treatment Period 1. The first 2 doses of the investigational product (6 mg/kg orally) will be administered during Visit 2 and the remaining doses will be administered at home. Patients will receive investigational product up to Day 28 (Treatment Period 1). Following Treatment Period 1, Treatment Period 2 (Dose Tapering Period) will begin on Day 29 and the dose will be reduced by half for all patients. On Day 35, the dose will be reduced by half again, and on Day 42, the investigational product will be stopped.
- i. Prior medications will be recorded during the Screening Period. All medications taken by patients after Screening Period until the completion of the final Follow-Up visit will be documented as concomitant medications.
- j. Seizure diary will be distributed on the Screening Period visit (Visit 1). The investigator will ensure that the seizure diary is being completed. The investigator will also review seizure counts to make sure seizures are not increasing. [REDACTED]
- k. Details regarding PK blood sampling are provided in [Table 3–2](#).
- l. Urine sampling for PK assessment will be collected by using a plastic urine collection bag following the morning dosing of investigational product on Day 1 and Day 21 (Visit 4 [ $\pm$  2 days]).
- m. The Clinical Global Impression of Change is completed by both the Investigator and the Caregiver. CGI-C on Day 1 is performed prior to dosing.

Source: Protocol Final Version 2.0, dated 15 September 2020.

### **3.2 Study Population**

This study will enroll male and female subjects meeting the following criteria: they are between 6 months through 36 months of age at the time of informed consent, have a clinical diagnosis of IS, confirmed by video-EEG analysis, and hypsarrhythmia on EEG at screening according to the BASED scale score.

### **3.3 Evaluations at Screening and Check-in**

The screening period will be a maximum of 28 days and will include Day -28 to Day -6 prior to first dose of study drug. Refer toError! Reference source not found. Table 3-1 Schedule of EventError! Reference source not found. Table 3-1 Schedule of Event for screening and check-in procedures.

### **3.4 Randomization and Treatment Assignments**

This is an open-label study.

### **3.5 Study Drug Administration**

Investigational product will be administered at 6 mg/kg, orally twice daily, once in the morning and 12 hours following the morning dose during the first 7 days of Treatment Period 1. Starting from the PM dose on the day of Visit 3, the dose will be escalated and patients will receive the investigational product at a dose of 9 mg/kg orally twice daily. Starting on Day 15, the dose will be escalated again and patients will receive the investigational product at a dose of 15 mg/kg orally twice daily until the end of Treatment Period 1. Each dose of the investigational product will be administered after at least a 2-hour fast. Food can be given 2 hours after dosing.

### **3.6 Compliance**

Treatment compliance will be discussed with the patient's legal representative (parent[s]/caregiver[s]) by the study site staff at each visit, and noncompliance will be noted based on details the study site obtains at the patient visits. Any missed dose against the instructions will be recorded in the electronic case report form (eCRF).

### **3.7 Pharmacokinetic Sampling Schedule**

PK blood sampling will be performed at time points mentioned in [Table 3-2](#) Steady State Pharmacokinetic Sampling Time Points.

**Table 3-2 Steady State Pharmacokinetic Sampling Time Points**

Study Period		
Visit	Study Days	Blood Sampling Time Points a
2 b	1	

• 0.5-1.5 hours post-AM dose

• 4-6 hours post-AM dose

• 8 hours post-AM dose time point and pre-PM dose

4 b	21	

• 0.5-1.5 hours post-AM dose

• 4-6 hours post-AM dose

• 8 hours post-AM dose time point and pre-PM dose

a. The PK blood sampling scheme may be modified on a case-by-case basis so as not to exceed a total blood draw limit of 8 mL/kg over 56 days, to a maximum blood draw of 50 mL. Note that the total blood drawn accounts for both blood draws for PK assessment as well as other assessments (i.e., clinical laboratory assessments).

b. The AM dose should be administered at the clinical site prior to the PK blood sampling on Visit 2 & 4.

Urine sampling for PK assessment will be collected for the morning dosing of investigational product on Day 1 and Day 21 (Visit 4 [ $\pm$  2 days]).

Pharmacokinetic blood and urine samples may be used for future exploratory purposes outside of this study.

### **3.8 Evaluation of Treatment Safety**

#### **3.8.1 Adverse Events**

An AE is defined as any untoward medical occurrence in a patient enrolled into this study regardless of its causal relationship to the investigational product. The patient's legal representative (parent[s]/caregiver[s]) will be instructed to contact the investigator at any time if any symptoms develop.

A TEAE is defined as any event not present before exposure to the investigational product or any event already present that worsens in either intensity or frequency after exposure to the investigational product.

All AEs will be reported or observed during the study will be recorded on the AE form in the eCRF. The AE and SAE reporting period begins after administration of study drug through the follow up visit. The Investigator will follow-up on all AEs observed or reported by the subject up to the end of the reporting period unless the event stabilizes and follow-up is no longer necessary. The Investigator will follow-up on SAEs until they are considered resolved or the outcome is known.

The following details will be collected for AEs: description of the AE, onset date/time, action taken with study drug (dose not changed, drug interrupted, drug withdrawn, dose increased, not applicable, or unknown), date/time of resolution, any additional treatment given, outcome

(recovered/resolved, not recovered/not resolved, recovered/resolved with sequelae, recovering/resolving, fatal or unknown), severity (mild, moderate, severe), seriousness (yes, no), relationship to study drug (unrelated, possibly, probably, definitely related or unknown), and whether the AE causes early termination of the subject.

The severity of AEs will be categorized as follows:

- Mild: These events require minimal or no treatment and do not interfere with the patient's daily activities.
- Moderate: An AE that is sufficiently discomforting to interfere with normal activities.
- Severe: These events interrupt a patient's usual daily activity and may require systemic drug therapy or other treatment. Severe events are usually incapacitating.

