The investigator will also contact the parent/caregiver by telephone on Day 12, or Day 13 or Day 14 to review seizure counts and to assess the patient's status using the above questions.

Patients will return to the study clinic on Day 7 (Visit 3 [\pm 2 days]). Starting from the PM dose on the day of Visit 3, the dose will be escalated and patients will receive the investigational product at a dose of 9 mg/kg orally twice daily. Starting on Day 15, the dose will be escalated again and patients will receive the investigational product at a dose of 15 mg/kg orally twice daily until the end of Treatment Period 1.

At Visit 2 and each visit thereafter, a record of the incidence and severity of TEAEs and SAEs will be collected and this will serve as a primary outcome criterion for this study. Other safety-related parameters such as 12-lead electrocardiogram (ECG), hematology, chemistry, physical examination, and vital signs will also be assessed at specified visits. Seizure diaries will be collected to assess spasms count prior to each visit following Visit 1.

Video-EEG will be repeated at Day 28 (Visit 5 [\pm 2 days]) (overnight video-EEG), following Treatment Period 1 for the assessment of spasms and hypsarrhythmia.

[figure not shown]
At Visit 2 and each visit thereafter, Clinical Global Impression of Change (CGI-C) will be collected from both the investigator and the parent/caregiver.

Treatment Period 2: Dose Tapering Period (Days 29 to 42):

The full dose of the investigational product will be continued until Day 28. At the start of the Dose Tapering Period on Day 29, the dose will be reduced by half. On Day 35, the dose will be reduced by half again, and on Day 42, the investigational product will be stopped. Patients will return to the study clinic on Day 42 (Visit 6 [\pm 5 days]). Refer to [Appendix 13.1](#) for list of tests/procedures.

Follow-Up Period (Day 43 to 56):

Patients will return to the study clinic on Day 56 (Visit 7 [\pm 5 days]). Refer to Appendix 13.1 for list of tests/procedures.

Figure 3-1 Study Design**3.1.1 Rationale of Study Design**

This open-label, multicenter study design allows the investigational product to be given as either add-on therapy or monotherapy. The design and choice of study population for this Phase 2 clinical study is based on the need to provide initial safety, tolerability, PK, and efficacy outcomes of the investigational product for future clinical studies.

4 Patient Selection and Withdrawal Criteria

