6.1.5.3 Eliciting and Documenting Adverse Events

Adverse events will be assessed from the time the patient's legal representative (parent[s]/caregiver[s]) signs the ICF until and including the Follow-Up visit, 14 days after the last dose of the investigational product.

Serious AEs that occur more than 14 days after the last dose of the investigational product need not be reported unless the investigator considers them related to the investigational product.

At every study visit, the patient's legal representative (parent[s]/caregiver[s]) will be asked a standard nonleading question to elicit any medically-related changes in the patient's well-being. They will also be asked if the patient has been hospitalized, had any accidents, taken any new medications, or changed concomitant medication regimens (both prescription and OTC medications).

In addition to patient observations, AEs identified from any study data (e.g., laboratory values, physical examination findings, and ECG changes) or identified from review of other documents (e.g., seizure diaries) that are relevant to patient safety will be documented on the AE page in the eCRF.

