6.1.5.4 Reporting Adverse Events

All AEs reported or observed during the study will be recorded on the AE page in the eCRF. Information to be collected includes drug treatment, dose, event term, time of onset, investigator-specified assessment of severity and relationship to the investigational product, time of resolution of the event, seriousness, any required treatment or evaluations, and outcome. Adverse events resulting from concurrent illnesses, reactions to concurrent illnesses, reactions to concurrent medications, or progression of disease states must also be reported. All AEs will be followed to adequate resolution. The Medical Dictionary for Regulatory Activities (MedDRA) will be used to code all AEs.

Any medical condition that is present at the time that the patient is screened but does not deteriorate should not be reported as an AE. However, if it deteriorates at any time during the study, it should be recorded as an AE.

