#### **4 CHANGES IN THE CONDUCT OF THE STUDY OR PLANNED ANALYSIS**

There are no changes in the study conduct or analysis plans relative to the study protocol.

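### The SAP starts AE and SAE reporting after the first dose but the protocol starts it at consent, so events arising in between may go unrecorded and some TEAEs may be misjudged

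*SAP*

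**What the plan says.** The two documents give different start points for AE collection.

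- **Protocol 6.1.5.3:** "Adverse events will be assessed from the time the patient's legal representative (parent[s]/caregiver[s]) signs the ICF until and including the Follow-Up visit".
- **SAP 3.8.1:** "The AE and SAE reporting period begins after administration of study drug through the follow up visit".
- **SAP section 4:** "There are no changes in the study conduct or analysis plans relative to the study protocol". SAP section 1 likewise describes the SAP as consistent with the protocol's statistical section.

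Other parts of the protocol lean towards the later start. In Protocol 13.1 the row "Adverse event monitoring" is empty under Screening and marked from Visit 2 onward, and SAP Table 3-1 repeats this. Protocol 3.1 says: "At Visit 2 and each visit thereafter, a record of the incidence and severity of TEAEs and SAEs will be collected".

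Both documents define a TEAE by its state before exposure. It is either an event that was absent before exposure or, in the second limb, "any event already present that worsens in either intensity or frequency after exposure to the investigational product".

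**The concern.** The incidence of TEAEs is the primary endpoint. Both limbs of its definition compare the patient after the first dose with the patient before it, so they need a record of what was present, and how severe it was, just before dosing.

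Conditions present at Visit 1 are covered by the medical history, and Protocol 6.1.5.4 keeps unchanged ones out of the AE data: "Any medical condition that is present at the time that the patient is screened but does not deteriorate should not be reported". Medical history is scheduled only at Visit 1. An illness that begins after Visit 1 and before the first dose is therefore not scheduled for capture there, and under SAP 3.8.1 it also falls outside the AE period. If it continues past Day 1 it could be entered as new. If it then worsens, there may be no pre-dose severity to compare with.

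The same sentence covers SAEs. Screening includes an overnight video-EEG stay, and Protocol 6.1.5.5 requires SAE reports within 24 hours with no exemption for the pre-dose interval.

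**Working it through.** The plan gives no figure to reproduce, so the check is mainly a comparison of text.

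**1. Which places support which start?**

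- *Start at consent, or pre-dose AE records assumed:*
  - Protocol 6.1.5.3 starts at signature of the consent form.
  - Protocol 7.7.1 promises a listing that includes non-treatment-emergent AEs.
  - SAP 7.2.1 has a category for pre-treatment AEs.
  - SAP Listing 16.2.7.1 covers all AEs.
- *Start at or after first dose:*
  - SAP 3.8.1.
  - The empty Screening cell in Protocol 13.1 and in SAP Table 3-1.
  - Protocol 3.1, which collects from Visit 2. Its scripted caregiver questions, which include one on possible AEs, begin on Day 2.

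The SAP thus conflicts with the protocol and with its own outputs, which need records that SAP 3.8.1 places outside the reporting period.

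**2. How long is the gap?** Screening runs from Day -28 to Day -6 and dosing starts on Day 1. Under the SAP 7.1 study-day convention (event date minus first dose date for earlier dates), these are 28 and 6 days before the first dose. Protocol 3.1 expects Screening to be appreciably shorter than 28 days and makes patients eligible for dosing on the 6th day after screening is complete. The gap between consent and first dose is therefore at least about 6 days and at most 28, usually well short of the maximum.

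**3. What must happen for the endpoint to be affected?** An event must begin in the gap, persist to Day 1, and either be entered with a post-dose onset or worsen without a pre-dose severity on file. Events that resolve before dosing cannot become TEAEs.

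The partial-date rule in SAP 7.2.1 adds a smaller route. An AE start imputed to the first of the month or of the year that falls before the first dose is moved to the first dose date. This pushes incompletely dated pre-dose events towards treatment-emergent.

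**4. Size per patient.** The safety set is all dosed patients, planned at about 35.

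- One patient wrongly counted, with no other TEAE: 1/35 = 0.0286, or 2.9 percentage points on overall incidence.
- One patient wrongly counted who has another TEAE: no change in overall incidence. The preferred-term row still moves by 2.9 points, unless the patient already counts in that row.
- A missed worsening acts in the opposite direction.

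The documents give no rate of pre-dose events, of persistence to Day 1 or of non-recording, so no total can be calculated.

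**The case against.** The strongest reply is that sites work to the protocol and the SAP only governs analysis. Protocol 6.1.5.3 is explicit about consent, Protocol 6.1.5.4 has all AEs during the study recorded, and the SAE duty has no pre-dose exemption. This stands in part: the SAP sentence alone would not stop a site recording a screening event. But the schedule of events and Protocol 3.1 are also protocol text, they are what sites use day to day, and they point to Visit 2.

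The second reply is that a pre-dose reference exists. A physical and neurological examination precedes the first dose. A standard question is asked at every visit. Each AE has an onset time. Medications are reviewed at Visits 1 and 2, and the seizure diary starts the day after Visit 1. An illness first elicited at Visit 2 with its true onset date would be classified correctly. This also stands, and it limits the risk. It does not remove it: an examination can miss an intermittent event and does not itself supply AE onset and severity, and the diary covers seizures only.

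The third reply is that the analysis already separates pre-dose events. SAP 7.12.1 ties a TEAE to onset or worsening after dosing starts, and pre-dose events are to be listed. This is correct, so no new classification rule is needed. It works only on events that have been recorded.

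A reader might infer that TEAE status cannot be judged at all, or might apply an assumed illness rate to the screening interval and read the result as misclassified patients. The documents support neither. The safeguards above allow correct classification in many cases. Patients with any event starting in Screening are also a much wider group than those whose event persists, goes unrecorded and is then misdated.

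**Conclusion.** The contradiction is real and undeclared, and SAP 3.8.1 is wrong as written against Protocol 6.1.5.3. The consequence is conditional. If sites or the database follow the later start, AEs and SAEs between consent and first dose may be lost, and some persisting events may be misjudged as new or as not worsened.

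The 2.9-point figure assumes 35 dosed patients and applies to overall incidence only for a patient with no other TEAE. The documents do not show that screening SAEs will go unreported; they show inconsistent instructions that leave room for it. In an open-label, descriptive study with no formal testing, this is minor to moderate. It is worth correcting because it touches the primary endpoint and events not recorded at the time may not be recoverable later.

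**What to change.** - **SAP 3.8.1:** define the AE and SAE period as running from signature of the consent form through the Follow-Up visit.
- **Both schedules of events:** mark AE monitoring across the Screening Period. A mark at Visit 1 alone would not cover the interval up to dosing, so add a note that events since consent are elicited at Visit 2 before the first dose.
- **Protocol 3.1:** reconcile the Visit 2 start with Protocol 6.1.5.3.
- **SAP 7.12.1:** state that recorded pre-dose events and their severity are the reference for judging worsening. Listing them as non-treatment-emergent is already planned and needs no change.
- **Database check:** confirm that the AE page accepts onset dates between consent and first dose.

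The cost is a short SAP edit before database lock, a small protocol amendment for the schedule and Protocol 3.1, and slightly more AE data entry at Screening. Sample size and analysis methods are unaffected.
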